Acutely symptomatic (NeuroARC Type 3) without CNS injury, including:³

Type 3.a TIA

Transient focal neurological signs or symptoms (lasting <24 h) presumed to be due to focal brain, spinal cord, or retinal ischemia, but without evidence of acute infarction by neuroimaging or pathology (or in the absence of imaging)

Type 3.b Delirium without CNS injury

Transient nonfocal (global) neurological signs or symptoms (variable duration) without evidence of cell death by neuroimaging or pathology

Neurological events

See “stroke (VARC-2 defined)”, “Overt CNS Injury”, “Covert CNS Injury”, “Neurological dysfunction without CNS injury”, “CNS infarction”, and “CNS hemorrhage”

New neurologic impairment	NIHSS worsening at post-procedure (2-5 days post-procedure) accompanied by the presence of cerebral ischemic lesions.
NIHSS worsening	An NIHSS score increase from baseline to follow-up.
NYHA (New York Heart Association) functional capacity	
Classified as¹¹⁰:
 
Class I. Patients with cardiac disease but without resulting limitation of physical activity. Ordinary physical activity does not cause undue fatigue, palpitation, dyspnea, or anginal pain.
 
Class II. Patients with cardiac disease resulting in slight limitation of physical activity. They are comfortable at rest. Ordinary physical activity results in fatigue, palpitation, dyspnea, or anginal pain.
 
Class III. Patients with cardiac disease resulting in marked limitation of physical activity. They are comfortable at rest. Less than ordinary activity causes fatigue, palpitation, dyspnea, or anginal pain.
 
Class IV. Patients with cardiac disease resulting in inability to carry on any physical activity without discomfort. Symptoms of heart failure or the anginal syndrome may be present even at rest. If any physical activity is undertaken, discomfort is increased.

Overt CNS Injury	
Acutely symptomatic brain or spinal cord injury (NeuroARC Type 1), including³:
 
Type 1.a Ischemic stroke
 
Sudden onset of neurological signs or symptoms fitting a focal or multifocal vascular territory within the brain, spinal cord, or retina, that:
 
 1) Persist for ≥ 24 h or until death, with pathology or neuroimaging evidence that demonstrates either: 
 a) CNS infarction in the corresponding vascular territory (with or without hemorrhage); or b) Absence of other apparent causes (including hemorrhage), even if no evidence of acute ischemia in the corresponding vascular territory is detected 
or
 
 2) Symptoms lasting < 24 h, with pathology or neuroimaging confirmation of CNS infarction in the corresponding vascular territory. Note: When CNS infarction location does not match the transient symptoms, the event would be classified as covert

CNS infarction (Type 2a) and a TIA (Type 3a), but not as an ischemic stroke.

Signs and symptoms consistent with stroke typically include an acute onset of 1 of the following: focal weakness and/or numbness; impaired language production or comprehension; homonymous hemianopia or quadrantanopsia; diplopia; altitudinal monocular blindness; hemispatial neglect; dysarthria; vertigo; or ataxia.

Subtype 1.a.H Ischemic stroke with hemorrhagic conversion

Ischemic stroke includes hemorrhagic conversions. These should be subclassified as Class A or B when ischemic stroke is the primary mechanism and pathology or neuroimaging confirms a hemorrhagic conversion.

Class A (Petechial hemorrhage): Petechiae or confluent petechiae within the infarction or its margins, but without a space-occupying effect

Class B (Confluent hemorrhage): Confluent hemorrhage or hematoma originating from within the infarcted area with space-occupying effect

Type 1.b Symptomatic intracerebral hemorrhage

Rapidly developing neurological signs or symptoms (focal or global) caused by an intraparenchymal, intraventricular, spinal cord, or retinal collection of blood, not caused by trauma

Type 1.c Symptomatic subarachnoid hemorrhage

Rapidly developing neurological signs or symptoms (focal or global) and/or headache caused by bleeding into the subarachnoid space, not caused by trauma

Type 1.d Stroke, not otherwise specified

An episode of acute focal neurological signs or symptoms and/or headache presumed to be caused by CNS ischemia or CNS hemorrhage, persisting ≥ 24 h or until death, but without sufficient evidence to be classified as either (i.e., no neuroimaging performed)

Type 1.e Symptomatic hypoxic-ischemic injury

Nonfocal (global) neurological signs or symptoms due to diffuse brain, spinal cord, or retinal cell death (confirmed by pathology or neuroimaging) in a nonvascular distribution, attributable to hypotension and/or hypoxia

Per Treatment (PT) population

The PT population is defined as subjects in the Intervention group in whom device positioning is maintained until final

procedure with complete cerebral coverage, and all Control group subjects.

Procedure success

Technical success in the absence of any investigational device-related or investigational procedure-related in-hospital procedural safety events.

Prosthetic Valve DysfunctionDefined according to VARC criteria in the table below:³⁵**Prosthetic Valve Dysfunction**

Prosthetic aortic valve stenosis*			
	Normal	Mild Stenosis	Moderate/Severe Stenosis
Quantitative Parameters (Flow-dependent)†			
Peak velocity	<3 m/s	3-4 m/s	>4 m/s
Mean gradient	<20 mmHg	20-40 mmHg	>40 mmHg
Quantitative Parameters (Flow-independent)			
Doppler velocity index‡	>0.35	0.35-0.25	<0.25
Effective orifice area¶	>1.1 cm ²	1.1-0.8 cm ²	<0.8 cm ²
Effective orifice area§	>0.9 cm ²	0.9-0.6 cm ²	<0.6 cm ²
Prosthesis-patient mismatch (PPM)			
	Insignificant	Moderate	Severe
Indexed effective orifice area**	>0.85 cm ² /m ²	0.85-0.65 cm ² /m ²	<0.65 cm ² /m ²
Indexed effective orifice area††	>0.70 cm ² /m ²	0.90-0.60 cm ² /m ²	<0.60 cm ² /m ²
Prosthetic aortic valve regurgitation			
	Mild	Moderate	Severe
Semi-quantitative Parameters			
Diastolic flow reversal in the descending aorta—PW	Absent or brief early diastolic	Intermediate	Prominent, holodiastolic
Circumferential extent of prosthetic valve paravalvular regurgitation (%)¶¶¶	<10	10-29	≥30
Quantitative Parameters‡			
Regurgitant volume (ml/beat)	<30	30-59	≥60
Regurgitant fraction (%)	<30	30-49	≥50
EROA (cm ²)	0.10	0.10-0.29	≥0.30

*In conditions of normal or near normal stroke volume (50–70 mL)

†These parameters are more affected by flow, including concomitant aortic regurgitation

‡For LVOT >2.5 cm, significant stenosis criteria is <0.20

¶Use in setting of BSA ≥1.6 cm² (note: dependent on the size of the valve and the size of the native annulus)§Use in setting of BSA <1.6 cm²**Use in setting of BMI <30 kg/cm²††Use in setting of BMI ≥30 kg/cm²

¶¶¶Not well-validated and may overestimate severity compared to quantitative Doppler

Serious Adverse Device Effect (SADE)

A serious adverse device effect is an adverse device effect that has resulted in any of the consequences characteristic of a serious adverse event.

Serious Adverse Event (SAE)

A serious adverse event is an adverse event that:

1. Led to a death
2. Led to a serious deterioration in the health of the subject that:
 - a. Resulted in a life-threatening illness or injury
 - b. Resulted in a permanent impairment of a body structure or a body function
 - c. Required in-patient hospitalization or prolongation of existing hospitalization
 - d. Resulted in medical or surgical intervention to prevent life-threatening illness or injury or permanent impairment to body structure or a body function
3. Led to fetal distress, fetal death or a congenital abnormality or birth defect.

Stroke (VARC-2 defined)Diagnostic criteria:

- Acute episode of a focal or global neurological deficit with at least one of the following: change in level of consciousness, hemiplegia, hemiparesis, numbness or sensory loss affecting one side of the body, dysphasia or aphasia, hemianopia, amaurosis fugax, or other neurological signs or symptoms consistent with stroke
- Stroke: duration of a focal or global neurological deficit ≥ 24 h; OR < 24 h if available neuroimaging documents a new hemorrhage or infarct; OR the neurological deficit results in death
- TIA: duration of a focal or global neurological deficit < 24 h, any variable neuroimaging does not demonstrate a new hemorrhage or infarct
- No other readily identifiable non-stroke cause for the clinical presentation (e.g. brain tumor, trauma, infection, hypoglycemia, peripheral lesion, pharmacological influences), to be determined by or in conjunction with designated neurologist (Patients with non-focal global encephalopathy will not be reported as a stroke without unequivocal evidence of cerebral infarction based upon neuroimaging studies [CT scan or brain MRI]).
- Confirmation of the diagnosis by at least one of the following:
 - Neurologist or neurosurgical specialist

- Neuroimaging procedure (CT scan or brain MRI), but stroke may be diagnosed on clinical grounds alone

Stroke classification:

- Ischemic – An acute episode of focal cerebral, spinal, or retinal dysfunction caused by infarction of central nervous system tissue
- Hemorrhagic – An acute episode of focal or global cerebral or spinal dysfunction caused by intraparenchymal, intraventricular, or subarachnoid hemorrhage
- A stroke may be classified as undetermined if there is insufficient information to allow categorization as ischemic or hemorrhagic

Stroke definitions (Modified Rankin Scale assessments should be made by qualified individuals according to a certification process):

- Disabling stroke – a mRS score of 2 or more at 90 days and an increase of at least one mRS category from an individual's pre-stroke baseline
- Non-disabling stroke – a mRS score of less than 2 at 90 days or one that does not result in an increase of at least one mRS category from an individual's pre-stroke baseline

Successful device deployment

Ability to access the aortic arch with the TriGuard HDH or TriGUARD 3 delivery catheter and deploy the device from the delivery catheter into the aortic arch.

Successful device retrieval

Ability to retrieve the TriGuard device and remove the TriGuard CEPD.

TAVI device success

Equivalent to the VARC definition¹¹¹ of “device success” for transcatheter aortic valves. Defined as:

- Absence of procedural mortality AND
- Correct positioning of a single prosthetic heart valve into the proper anatomical location AND
- Intended performance of the prosthetic heart valve (no prosthesis-patient mismatch (VARC-defined) and mean aortic valve gradient <20 mm Hg or peak velocity <3 m/s, AND no moderate or severe prosthetic valve regurgitation (VARC-defined)

Technical success

Successful TriGuard HDH or TriGUARD 3 device deployment, device positioning, and successful device retrieval in the absence of device interference

Total procedural time	Time elapsed between first arterial access and removal of the last catheter from the arterial access sheath
Unanticipated Adverse Device Effect (UADE)	
An unanticipated adverse device effect is any serious adverse effect on the health or safety or any life-threatening problem or death caused by, or associated with, a device, if that effect, problem, or death was not previously identified in nature, severity or degree of incidence in the investigational plan or application (including a supplementary plan or application), or any other unanticipated serious problem associated with a device that relates to the rights, safety or welfare of subjects.
 
NOTE: An anticipated serious adverse device effect (ASADE) is a serious adverse device effect which by its nature, incidence, severity, or outcome has been identified in the investigational plan or application (including a supplementary plan or application).

Use Error	
Act or omission of an act that results in a different medical device response than intended by the manufacturer or expected by the user.
 
NOTE 1: Use error includes slips, lapses and mistakes. NOTE 2: An unexpected physiological response of the patient does not itself constitute a use error.

Vascular access site and access-related complications	
Major Vascular Complications:³⁵
 
 Any aortic dissection, aortic rupture, annulus rupture, left ventricle perforation, or new apical aneurysm/pseudo-aneurysm OR Access site or access-related vascular injury (dissection, stenosis, perforation, rupture, arterio-venous fistula, pseudoaneurysm, hematoma, irreversible nerve injury, compartment syndrome, percutaneous closure device failure) leading to death, life-threatening or major bleeding, visceral ischemia or neurological impairment OR Distal embolization (non-cerebral) from a vascular source requiring surgery or resulting in amputation or irreversible end-organ damage OR The use of unplanned endovascular or surgical intervention associated with death, major bleeding, visceral ischemia or neurological impairment OR Any new ipsilateral lower extremity ischemia documented by patient symptoms, physical exam, and/or decreased or absent blood flow on lower extremity angiogram OR Surgery for access site-related nerve injury OR

- Permanent access site-related nerve injury

Minor vascular complications:

- Access site or access-related vascular injury (dissection, stenosis, perforation, rupture, arterio-venous fistula, pseudoaneurysms, hematomas, percutaneous closure device failure) **not leading to** death, life-threatening or major bleeding, visceral ischemia or neurological impairment OR
- Distal embolization treated with embolectomy and/or thrombectomy and not resulting in amputation or irreversible end-organ damage OR
- Any unplanned endovascular stenting or unplanned surgical intervention not meeting the criteria for a major vascular complication OR
- Vascular repair or the need for vascular repair (via surgery, ultrasound-guided compression, transcatheter embolization, or stent-graft)

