5.4.2.1.2 Secondary Safety Endpoints

The following safety endpoints will be evaluated in-hospital and at 30 days. Overall event rates will be reported by treatment group. In the Intervention and Roll-In groups, all safety endpoints will be adjudicated for their relationship to the investigational device and/or the investigational procedure by an independent Clinical Events Committee (§11.1):

- In-hospital procedural safety, defined as the composite of the following Major Adverse Cardiovascular and Cerebrovascular Events (MACCE):
 - All-cause mortality
 - All stroke (disabling and non-disabling)
 - Life threatening (or disabling) bleeding
 - Acute kidney injury – Stage 2 or 3 (including renal replacement therapy)
 - Major vascular complications
- TAVI device success (VARC), evaluated in-hospital, defined as:
 - Absence of procedural mortality AND
 - Correct positioning of a single prosthetic heart valve into the proper anatomical location AND
 - Intended performance of the prosthetic heart valve (no prosthesis-patient mismatch (VARC-defined) and mean aortic valve gradient <20 mm Hg or peak velocity <3 m/s, AND no moderate or severe prosthetic valve regurgitation (VARC-defined) (site-reported)
- General safety, defined as the composite of the following adverse events (each VARC-2 defined):
 - All-cause mortality
 - All stroke (disabling and non-disabling)
 - Acute kidney injury – Stage 3 (including renal replacement therapy)
- Mortality [evaluated in-hospital and at 30 and 90 days]:
 - All-cause mortality
 - Cardiovascular mortality

- Neurologic event related mortality
 - Non-cardiovascular mortality
- Myocardial infarction:
 - Peri-procedural MI (≤ 72 hours after the index procedure)
 - Spontaneous MI (> 72 hours after the index procedure)
- Neurological Events (component and composite):
 - Stroke (VARC-2 defined) **[evaluated in-hospital and at 30 and 90 days]**
 - Ischemic stroke
 - Hemorrhagic stroke
 - Undetermined
 - Disabling Stroke (VARC-2 defined) **[evaluated in-hospital and at 30 and 90 days]**
 - Non-disabling stroke (VARC-2 defined) **[evaluated in-hospital and at 30 and 90 days]**
 - Transient ischemic attack (TIA) (VARC-2 defined)
 - Overt CNS Injury (NeuroARC defined Type 1) **[evaluated in-hospital and at 30 and 90 days]**
 - Covert CNS Injury (NeuroARC defined Type 2)
 - Neurological dysfunction without CNS injury (NeuroARC defined Type 3)
 - CNS infarction (NeuroARC defined composite neurological endpoint)

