7.5 Post-procedure Follow-up

The procedure is considered complete once the last guiding catheter has been removed from the patient and the patient is off the table. Thereafter, if a guiding catheter is re-introduced, this is considered a repeat intervention, which must be documented.

The post-procedure follow up will consist of:

- Physical examination including ischemic / anginal status (CCS or silent ischemia), heart rate, and blood pressure
- Documentation of any adverse events/ serious adverse events occurring since the point of enrollment
- Current concomitant medications documentation, including antiplatelet and anticoagulant therapy
- Routine laboratory tests including:
 - Hematology - hemoglobin, hematocrit, platelet count, white blood cell count
 - Chemistry - creatinine. Serum creatinine should be measured within 48 hours post-procedure in all subjects. Subjects with elevated serum creatinine ($\geq 1.5 \times$ baseline OR > 0.3 mg/dL [> 26.4 mmol/L]) should have continued assessments to 7 days post-procedure or until discharge (whichever occurs first) to assess acute kidney injury.
 - Cardiac enzymes: CK/CKMB or Troponin (preferably CKMB isoenzyme) will be measured when clinically indicated. If cardiac biomarkers are elevated, they should be repeated per local standard of care.
- A 12-lead ECG, to be completed within 24 hours post-procedure or prior to hospital discharge (whichever occurs first)
- If echocardiography (transthoracic or transesophageal) was performed after TAVR prosthesis implantation as part of the standard of care, the relevant parameters (including mean aortic valve gradient, peak velocity, and degree of prosthetic aortic

valve regurgitation) must be captured on the eCRF for evaluation in-hospital TAVI device success (§□)

- Diffusion-weighted MRI of the brain 2 to 5 days (≥ 48 to < 144 hours) post-procedure
- NIH Stroke Scale (NIHSS). Neurologic status evaluation using the NIH stroke scale shall be performed 2 to 5 days (≥ 48 to < 144 hours) post-procedure and during each follow-up assessment. The examination must be performed by a neurologist or a clinical designee (e.g. neurology fellow).
- Modified Rankin Scale (mRS) shall be performed 2 to 5 days (≥ 48 to < 144 hours) post-procedure and during each follow-up assessment. The assessment must be performed by a neurologist or a clinical designee (e.g. neurology fellow).

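### The mismatch row for BMI of 30 or more puts indexed orifice areas above 0.70 and up to 0.90 cm²/m² in two categories, so TAVI device success is ambiguous for those patients

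*Combined protocol and SAP*

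**What the plan says.** The entry Prosthetic Valve Dysfunction in Appendix I (16.1) attributes its table to VARC criteria. The two mismatch rows, in cm²/m² of indexed effective orifice area, are:

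| Row | Insignificant | Moderate | Severe |
|---|---|---|---|
| BMI below 30 | above 0.85 | "0.85-0.65 cm ² /m ²" | below 0.65 |
| BMI 30 or more | above 0.70 | "0.90-0.60 cm ² /m ²" | below 0.60 |

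Footnotes choose the row: "Use in setting of BMI <30 kg/cm²" for the first and "Use in setting of BMI ≥30 kg/cm²" for the second.

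Mismatch enters one endpoint. Section 5.4.2.1.2 lists TAVI device success, assessed in hospital, with this component: "Intended performance of the prosthetic heart valve (no prosthesis-patient mismatch (VARC-defined". The same component closes with "no moderate or severe prosthetic valve regurgitation (VARC-defined) (site-reported", which marks the assessment as the site's own. Appendix I repeats the criterion under TAVI device success: "Intended performance of the prosthetic heart valve (no prosthesis-patient mismatch (VARC-defined) and mean aortic valve gradient <20 mm Hg".

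The data come from echocardiography done as standard of care. Where one was done, section 7.5 requires the eCRF to hold "the relevant parameters (including mean aortic valve gradient, peak velocity" and the degree of regurgitation. Orifice area is not named. Section 12.4.5.1.1 reports secondary safety endpoints descriptively in the As Treated population, with no hypothesis test.

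**The concern.** Grades in a classification table should be mutually exclusive. Here one row gives two grades for the same measurement, and they lie on opposite sides of the line that matters to the endpoint. The table holds the protocol's only mismatch criteria, so nothing else in the text resolves the conflict.

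What is at stake is whether one component of one secondary endpoint can be reproduced. Because the assessment is site-reported, two sites with identical echo findings in an obese patient could record different results and both follow the table. A programmer deriving the endpoint centrally would have to choose a column without guidance.

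**Working it through.** The plan gives no figure to reproduce here. The check is to apply each row as printed and count the grades that each value receives.

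**Inputs.** All come from the mismatch rows and footnotes in Appendix I (16.1), as set out above.

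**Step 1: BMI 30 or more.** A value x is Insignificant if x > 0.70, Moderate if 0.60 ≤ x ≤ 0.90, and Severe if x < 0.60. The first two conditions hold together when 0.70 < x ≤ 0.90. On a grid of 0.01 from 0.40 to 1.19:

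| x | Grades met |
|---|---|
| 0.55 | Severe |
| 0.60 | Moderate |
| 0.70 | Moderate |
| 0.71 | Insignificant and Moderate |
| 0.80 | Insignificant and Moderate |
| 0.90 | Insignificant and Moderate |
| 0.91 | Insignificant |

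All 20 grid values from 0.71 to 0.90 receive two grades. No other value does.

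**Step 2: BMI below 30.** With x > 0.85, 0.65 ≤ x ≤ 0.85 and x < 0.65, every grid value receives exactly one grade.

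**Step 3: width.** The overlap is 0.90 − 0.70 = 0.20 cm²/m². The printed Moderate band is 0.90 − 0.60 = 0.30. So 0.20 / 0.30, or two thirds of that band, is also Insignificant.

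**Step 4: effect on the endpoint.** Take an obese patient at 0.80 who meets every other part of device success. Read from the Insignificant column, the patient has no mismatch and is a success. Read from the Moderate column, the patient has mismatch and is a failure.

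**Step 5: does the unit misprint matter?** Since 1 m² = 10,000 cm², a BMI of 30 kg/m² is 30 / 10,000 = 0.003 kg/cm², and 60 kg/m² is 0.006. Taken literally, every patient falls in the row for BMI below 30, and the overlapping row is never used. Read in kg/m², as a cut-off of 30 requires, the row is used and the overlap remains. Correcting the unit therefore does not remove the defect.

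**The case against.** The strongest reply is that this is a typing slip in an appendix table taken from a published source, on a component of an endpoint that is only described. It lies outside the primary safety composite, the primary efficacy hierarchy and the sequence of hypothesis-driven secondary endpoints. That is correct and sets the severity. It does not remove the overlap, because the row is a working threshold in an endpoint definition.

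Four stronger readings are tempting, and the documents do not support them.

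- *The unit misprint sends obese patients to the wrong row.* This needs a reader to apply kg/cm² literally, which no one would do with a cut-off of 30. On that reading the overlapping row is also never used, so the two faults cannot act together. The similar misprint for body surface area belongs to the stenosis orifice-area rows, not to mismatch.
- *Device success is misclassified.* The documents show a definition with two answers. They show no patient who was wrongly classified.
- *A headcount can be given.* It would need the BMI and indexed-area distributions, neither of which is in the documents. It would also need the number of subjects whose standard-of-care echo reports orifice area, which need not be the 225 of the initial randomized cohort. Patients who fail on another component are not ambiguous either.
- *The eCRF lacks orifice area.* The list in 7.5 is introduced as an inclusion list, not a complete one, and the eCRF is not among the documents. It can only be said that the text does not ensure capture.

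A reader might also infer from the neighbouring row that Moderate should begin at 0.70. That is plausible, but the documents cannot show whether the 0.70 or the 0.90 is the misprint, or whether the cited source carries it.

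**Conclusion.** Wrong as written, and minor. In the row for BMI of 30 or more, indexed areas above 0.70 and up to and including 0.90 cm²/m² meet two exclusive grades, and an obese patient in that range can be scored either way on one component of TAVI device success. This rests on one reading, which the criterion's wording invites: Insignificant counts as no mismatch and Moderate counts as mismatch. The overlap itself needs no assumption. The number of subjects affected cannot be stated from the documents. No alpha, power, sample size or primary conclusion changes.

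**What to change.** 1. Reconcile the row for BMI of 30 or more with the cited VARC source so that its three grades do not overlap. Apply the reconciled row in the same way to all subjects, at all sites and in both phases.
2. Correct the footnote units to kg/m² for BMI and m² for body surface area.
3. In section 7.5 and the matching schedule footnotes, name effective orifice area among the echo parameters to be captured when the standard-of-care study reports it. Height and weight are already collected at baseline (section 7.2), so BMI and body surface area can be derived.

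The cost is a short appendix correction and at most one eCRF field filled from an echo already done. No additional procedure, visit or subject is needed.
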